4.2 Endpoints

4.2.1 Primary endpoint

Change from baseline in glycosylated haemoglobin (HbA_{1c}) (%) after 26 weeks

4.2.2 Supportive secondary endpoints

4.2.2.1 Supportive secondary efficacy endpoints

At 26 weeks:

- Responder (Yes/No) for HbA_{1c} after 26 weeks
 - HbA_{1c} < 7%*
 - HbA_{1c} < 7% without nocturnal (00:01-05:59) blood glucose (BG) confirmed symptomatic hypoglycaemia
- Change from baseline in fasting plasma glucose (FPG) after 26 weeks

* Key supportive secondary endpoint prospectively selected for disclosure (e.g. clinicaltrials.gov and EudraCT)

- Self-measured plasma glucose measurements (SMPG) after 26 weeks
 - Mean pre-breakfast measurements used for titration
 - 9-point profile
 - Post-prandial increments

At 38 weeks:

- Change from baseline in HbA_{1c} (%) after 38 weeks*
- Responder (Yes/No) for HbA_{1c} after 38 weeks:
 - HbA_{1c} < 7%*
 - HbA_{1c} < 7% without nocturnal (00:01-05:59) BG confirmed symptomatic hypoglycaemia
- Change from baseline in fasting plasma glucose (FPG) after 38 weeks
- Self-measured plasma glucose measurements (SMPG) after 38 weeks
 - Mean pre-breakfast measurements used for titration
 - 9-point profile
 - Post-prandial increments

4.2.2.2 Supportive secondary safety endpoints:

During 26 weeks:

- Number of nocturnal, treatment-emergent severe or BG confirmed symptomatic hypoglycaemic episodes during 26 weeks
- Number of nocturnal, treatment-emergent severe or BG confirmed hypoglycaemic episodes during 26 weeks
- Number of treatment emergent severe or BG confirmed symptomatic hypoglycaemic episodes during 26 weeks*
- Number of treatment-emergent severe or BG confirmed hypoglycaemic episodes during 26 weeks
- Number of nocturnal, treatment emergent severe or BG confirmed symptomatic hypoglycaemic episodes during maintenance (week 16-26)
- Number of nocturnal, treatment-emergent severe or BG confirmed hypoglycaemic episodes during maintenance (week 16-26)
- Number of treatment emergent severe or BG confirmed symptomatic hypoglycaemic episodes during maintenance (week 16-26)
- Number of treatment-emergent severe or BG confirmed hypoglycaemic episodes during maintenance (week 16-26)
- Total insulin dose at week 26
- Change in weight from baseline to week 26
- Incidence of treatment-emergent adverse events (TEAEs) from baseline to week 26

* Key supportive secondary endpoint prospectively selected for disclosure (e.g. clinicaltrials.gov and EudraCT)

- Change from baseline to week 26 in:
 - Physical examination
 - Vital signs (blood pressure and pulse)
 - Dilated fundoscopy or fundus photography
 - 12-lead electrocardiogram
 - Laboratory assessments
 - Haematology (haemoglobin, haematocrit, erythrocytes, thrombocytes, leucocytes)
 - Biochemistry (creatinine, alanine aminotransferase, aspartate aminotransferase, alkaline phosphatase, sodium, potassium, albumin, total bilirubin)
 - Insulin antibodies

During 38 weeks:

- Number of nocturnal, treatment emergent severe or BG confirmed symptomatic hypoglycaemic episodes during 38 weeks
- Number of nocturnal, treatment-emergent severe or BG confirmed hypoglycaemic episodes during 38 weeks
- Number of treatment emergent severe or BG confirmed symptomatic hypoglycaemic episodes during 38 weeks*
- Number of treatment-emergent severe or BG confirmed hypoglycaemic episodes during 38 weeks
- Total insulin dose at week 38
- Change in weight from baseline to week 38
- Incidence of treatment-emergent adverse events (TEAEs) during 38 weeks*
- Change from baseline to week 38 in:
 - Physical examination
 - Vital signs (blood pressure and pulse)
 - Dilated fundoscopy or fundus photography
 - 12-lead electrocardiogram
 - Laboratory assessments:
 - Haematology (haemoglobin, haematocrit, erythrocytes, thrombocytes, leucocytes)
 - Biochemistry (creatinine, alanine aminotransferase, aspartate aminotransferase, alkaline phosphatase, sodium, potassium, albumin, total bilirubin)
 - Insulin antibodies

* Key supportive secondary endpoint prospectively selected for disclosure (e.g. clinicaltrials.gov and EudraCT)

Supportive secondary patient reported health economics endpoints

- Change from baseline to week 26 for:
 - Health-related quality of life as evaluated by the SF-36v2®
 - Treatment related impact as evaluated by TRIM D
- Change from baseline to week 38 for:
 - Health-related quality of life as evaluated by the SF-36v2®
 - Treatment related impact as evaluated by TRIM-D

5 Trial design

5.1 Type of trial

This is a 38-week, multinational, open-label, randomised (1:1), controlled, parallel, treat-to-target trial in subjects with T2DM treated with basal insulin with or without OAD(s) in need of treatment intensification. The aim of the trial is to compare IDegAsp OD vs IGlar OD + IAsp OD with or without OAD(s) after 26 weeks of treatment. In addition, a comparison of a stepwise treatment intensification of 12 weeks with IDegAsp OD to BID vs. IGlar OD + IAsp 1 to 3 times daily will be performed.

Subjects will be randomised in a 1:1 manner into one of the stepwise treatment intensification arms below and treated as described in Section [5.3.3](#).

IDegAsp arm:

- Initial 26 weeks: IDegAsp OD administered at the largest meal each day ± OAD(s)
- Intensification period – Week 26-38: IDegAsp OD/BID administered at the largest meal(s) each day based on individual needs ± OAD(s)

IGlar + IAsp arm:

- Initial 26 weeks: IGlar OD administered in accordance with local labelling and IAsp OD administered at the largest meal ± OAD(s)
- Intensification period – Week 26-38: IGlar OD administered in accordance with local labelling and IAsp 1-3 times daily administered at main meals based on individual needs ± OAD(s)

The trial design is summarised schematically in [Figure 5–1](#)

[figure not shown]

Figure 5–1 Trial Design

Randomisation will be stratified based on the pre-trial basal insulin treatment regimen: OD or BID/TID dosing. Subjects on a BID/TID regimen will be shifted to OD dosing in accordance with the Titration Guideline, [Appendix A](#).

A population of subjects with HbA_{1c} between 7.0-10.0% (both inclusive) treated with any basal insulin with or without OAD(s), and thus not achieving the recommended treatment target, and therefore in need of treatment intensification has been chosen.

The duration of the trial will be approximately 44 weeks and includes:

- Screening Visit (V1)
- Randomisation Visit (V2)
- Weekly contacts (phone or clinic visits (V3-V40)) throughout the 38 weeks' treatment period, refer to flow chart (Section [2](#))
- Two Follow-up visits at 7-12 days (V41) and 30 days (P42) after the end of treatment (EOT) visit (V40)

5.2 Rationale for trial design

An open label trial design has been chosen as blinding is not feasible due to the different regimens in the two treatment arms.

The reason for stratifying according to pre-trial basal insulin dosing OD or BID/TID is to ensure that these sub-populations are equally represented in both arms. The treat to target design will be implemented using a very tight visit schedule in order to ensure optimal insulin titration based on SMPG values and to ensure improvement in glycaemic control in the treatment initiation period. The initial 26-week treatment period is expected to be sufficient to initiate and up-titrate the trial treatment to obtain data for evaluation of efficacy, safety and PROs.

Similarly the 12-week intensification period is expected to be sufficient to intensify and up-titrate the trial treatment to obtain data for evaluation of efficacy, safety and PROs.

The multinational approach is to ensure that the results are applicable for subjects with different demographic characteristics.

The primary endpoint HbA_{1c} is a laboratory parameter and consequently the probability of assessment bias is limited.

The two follow-up visits are included to ensure proper follow-up on subject safety after end of trial drug-treatment.

A 1-week interval between the EOT visit (V40) and the 7-day follow-up visit (V41) is necessary to allow for trial insulin 'washout' prior to measurement of insulin antibodies. Due to the much shorter duration of the type of basal insulins (NPH or biphasic insulin aspart 30 (BiAsp 30)) used in the 'washout' period, the levels of insulin will be lower at the sampling time point at the 7-day follow-up (V41). For insulin treatment in the 'washout' period, see Section [5.5](#).

A 30-day follow-up (P42) after last trial insulin treatment (V40) will be performed in order to collect information about antidiabetic treatment and adverse events (AEs) occurring between V41 and P42.

5.3 Treatment of subjects

Subjects with T2DM treated with any basal insulin with or without OAD(s) can enter the trial if they have an HbA_{1c} between 7.0-10.0% (both inclusive).

Subjects will attend a screening visit (V1) where inclusion and exclusion criteria will be assessed.

If eligible, subjects will be randomised to their trial insulin treatment at the randomisation visit (V2), refer to Sections [5.3.1](#) and [5.3.2](#).

At randomisation subjects must discontinue pre-trial insulin, SU and glinides. Treatment with other OADs should continue during the trial as described in Section [5.4](#).

For subjects in both treatment arms diet and exercise counselling should be continued as per the standard of care at the investigational site.

At the EOT visit (V40) subjects should be switched to ‘washout’ insulin as described in Section [5.5](#)

5.3.1 Treatment regimens arms

Subjects will be randomised into a 1: 1 manner as described in Section [5.1](#) into the two stepwise treatment intensification arms below and treated as described in Section [5.3.3](#):

IDegAsp arm:

- Initial 26 weeks: IDegAsp OD administered at the largest meal each day ± OAD(s)
- Intensification period – Week 26-38: IDegAsp OD/BID administered at the largest meal(s) each day based on individual needs ± OAD(s)

IGlar + IAsp arm:

- Initial 26 weeks: IGlar OD administered in accordance with local labelling and IAsp OD administered at the largest meal ± OAD(s)
- Intensification period – Week 26-38: IGlar OD administered in accordance with local labelling and IAsp 1-3 times daily administered at main meals based on individual needs ± OAD(s)

5.3.2 Trial insulin products

The below trial insulin products will be provided by Novo Nordisk A/S:

- Insulin degludec/insulin aspart (Ryzodeg[®]) 100 units/mL, 3 mL pre-filled pen (FlexTouch[®]), solution for subcutaneous injection, Novo Nordisk A/S
- Insulin glargine (Lantus[®]) 100 units/mL, 3 mL pre-filled pen (SoloStar[®]), solution for subcutaneous injection, Sanofi-Aventis
- Insulin aspart (NovoRapid[®]/NovoLog[®]), 100 units/mL, 3 mL pre-filled pen (FlexPen[®]), solution for subcutaneous injection, Novo Nordisk A/S

The subjects must be trained in how to handle the above pre-filled pen-devices when handed out the first time (refer to section [8.6.3](#)). For further information on trial insulin products, see Section [9](#).

5.3.3 Trial insulin treatment

Subjects will receive either IDegAsp OD or IGlar OD + IAAsp OD during the first 26 weeks and continue into a 12-week intensification period.

Subjects on a pre-trial BID/TID basal insulin regimen will be shifted to OD dosing in accordance with the Titration Guideline, [Appendix A](#).

For information about initial doses, area of injection, dosing time and the weekly dose adjustments during the initial treatment period (week 2-26), refer to the Titration Guideline, [Appendix A](#).

At week 26 (V28), subjects not achieving sufficient glycaemic control ($V27 \text{ HbA}_{1c} \geq 7\%$) will be further intensified from either IDegAsp OD to IDegAsp BID or IGlar OD + IAAsp OD to IGlar OD + IAAsp BID. Subjects in good glycaemic control ($V27 \text{ HbA}_{1c} < 7\%$) will continue their insulin treatment regimen.

At week 32 (V34), glycaemic control will be evaluated again, and subjects in good glycaemic control ($V33 \text{ HbA}_{1c} < 7\%$) will continue their insulin treatment regimen. Subjects on IDegAsp OD not reaching the glycaemic target ($V33 \text{ HbA}_{1c} \geq 7\%$) will be intensified to IDegAsp BID, whereas subjects in the IGlar arm not reaching glycaemic control will be intensified with one additional IAAsp dose to IGlar OD + IAAsp BID or TID daily for the remaining six weeks of the intensification period.

Information about doses, dosing time and dose adjustments during the treatment intensification period (week 27-38) can be found in the Titration Guideline, [Appendix A](#).

Information about insulin treatment in the ‘washout’ period between the EOT visit (V40) and the 7-day follow-up visit (V41) can be found in Section [5.5](#).

5.4 Oral antidiabetic treatment

Upon trial entry, subjects treated with any of the below allowed OADs should continue their treatment unchanged, meaning subjects should not:

- start treatment with any other antidiabetic treatment
- change the pre-randomisation OAD(s) dose or dosing frequency^{a)}
- start treatment with any medication known to interfere significantly with glucose metabolism

^{a)} However, for safety reasons, a decrease in the OAD(s) dose is allowed if deemed necessary by the investigator.

OADs are not considered trial products and will not be supplied by Novo Nordisk A/S, refer to Section [9.1](#).

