6.5 Rescue criteria

If any of the fasting SMPG values taken on three consecutive days or if any of the FPG samples analysed by the central laboratory exceed the limit of:

- 15.0 mmol/L (270 mg/dL) from baseline to end of week 12
- 13.3 mmol/L (240 mg/dL) from week 13 to end of week 38

and if no treatable inter current cause for the hyperglycaemia has been identified, the subject must be called for a confirmatory FPG measurement at a scheduled or unscheduled visit as soon as possible. A confirmatory FPG must be obtained and analysed by the central laboratory. If this FPG exceeds the limits described above, the trial product must be discontinued.

The subject should be prescribed alternative therapy at investigator's discretion, and be retained in the trial.

If prematurely withdrawn from trial drug, effort should be made to follow the procedures described in Section [8.1.11](#). Also refer to Section [5.5](#).

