6.6 Criteria for premature discontinuation of trial product

Efforts must be made so that subjects attend and complete all scheduled visit procedures. Subjects should stay in the trial irrespective of lack of adherence to randomised treatment, lack of adherence to visit schedule or missing assessments. Only subjects who decline any further contact with the site in relation to the trial will be considered as withdrawn from the trial (see Section [6.7](#)).

The subject may be prematurely discontinued from trial product at the discretion of the investigator due to a safety concern or if judged non-compliant with trial procedures.

The subject must be prematurely discontinued from trial product if the following applies:

1. Included in the trial in violation of any of the inclusion and/or exclusion criteria
2. Pregnancy
3. Intention of becoming pregnant
4. Initiation or significant change in concomitant medications for more than 14 calendar days which in the investigator's opinion could affect weight or glucose metabolism
5. Simultaneous participation in another clinical trial of an approved or non-approved investigational medicinal product
6. The fasting SMPGs values taken on three consecutive days or any FPG samples analysed by the central laboratory exceeding the limit of (refer to section [6.5](#)):
 - 15.0 mmol/L (270 mg/dL) from baseline to end of week 12
 - 13.3 mmol/L (240 mg/dL) from week 13 to end of week 38

Subjects discontinued from trial product should be prescribed alternative therapy at investigator's discretion, and be retained in the trial.

For procedures to be performed for subjects discontinuing trial product prematurely, see Sections [8.1.11](#) and [5.5](#).

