2.3 Definition of analysis sets

The following analysis sets are defined in accordance with the ICH-E9²

- Full Analysis Set (FAS): includes all randomised subjects. In exceptional cases, subjects may be excluded. In such cases the elimination will be justified and documented. The statistical evaluation of the FAS will follow the intention-to-treat (ITT) principle and subjects will contribute to the evaluation “as randomised”.

- Per-Protocol (PP) analysis set: includes all subjects in the Full Analysis Set who fulfils the following criteria:
 - Have not violated any inclusion criteria
 - Have not fulfilled any exclusion criteria
 - Have a non-missing HbA_{1c} at screening or randomisation
 - Have at least one non-missing HbA_{1c} after 12 weeks of exposure
 - Have at least 12 weeks of exposure

Subjects in the PP will contribute to the evaluation “as treated”.

- Safety Analysis Set (SAS): includes all subjects receiving at least one dose of the investigational product or comparator. Subjects in the safety set will contribute to the evaluation “as treated”.
- Trial completer analysis set: Includes all randomised subjects who has attended either V40 on treatment, or V40A, 38 weeks after randomisation according to protocol .
- Treatment completer analysis set: Includes all randomised subjects who have completed the trial without discontinuation from randomised treatment.

Before data are released for statistical analysis, a review of all data will take place to ensure a sufficient data quality and to ensure the planned statistical analysis are applicable. Any data decisions not foreseen in the protocol will be documented before database lock.

Randomised subjects who are lost to follow up and where no exposure information of the investigational product or comparators is available after randomisation will be handled as unexposed.

The decision to exclude any subject or observation from the statistical analysis is the joint responsibility of the study group. The subjects or observations to be excluded, and the reasons for their exclusion will be documented before database lock. The subjects and observations excluded from the analysis sets, and the reasons for this, will be described in the clinical trial report.

Definition of the observation periods:

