In-trial: This observation period will include information collected at or after date of randomisation and up to the last scheduled subject-site contact. For subjects who withdraw their informed consent, or is lost to follow-up, the end of the in-trial period is defined as the date of the last scheduled subject-investigator contact (site or phone visit). In case a subject dies during the trial, the date of death will be the end-date of the in-trial observation period regardless of the above defined end-dates. This observation period will be used for estimating the effectiveness estimand.

On-treatment: This observation period is a subset of the in-trial observation period and represents the time period in which a subject is considered exposed to trial product. The period starts on day of the first dose of trial product and ends 7 days after last dose of trial product is taken

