- A tipping point analysis based on the FAS and the primary analysis for the primary estimand will be performed. In this analysis subjects who withdraw from the IDegAsp OD arm or have missing values at visit 26 are assumed to have an effect that is inferior to the de facto effect of IDegAsp OD. The extent of the inferiority (also termed a 'penalty') will be gradually increased to evaluate at which value IDegAsp OD is no longer non-inferior to IGlar OD + IA Sp OD. This penalty value, also known as the tipping point, corresponds to the hypothetical degree of efficacy deterioration in withdrawn subjects that would change the conclusion of non-inferiority.

Primary analysis for the secondary estimand

The secondary estimand will be estimated based on the FAS using post-baseline measurements up to and including week 26 from the on-treatment observation period. To estimate this estimand, the change from baseline in HbA_{1c} after 26 weeks of treatment will be analysed using the mixed model for Repeated Measurement (MMRM) method with a restricted maximum likelihood (REML). The model will include treatment, sex, previous insulin treatment regimen, previous OAD treatment and region as factors and baseline HbA_{1c} and age as covariates, all nested within visit. An unstructured covariance matrix for HbA_{1c} measurements within the same subject will be employed, assuming measurements from different subjects are independent.

The MMRM is a well-established method that accounts for the uncertainty pertaining to missing data. This analysis assumes that the missing data mechanism is missing at random (MAR). Under this assumption the statistical behaviour of the missing data (given the observed responses and model fixed effects and covariates) is assumed to be the same as the observed data.

In a non-inferiority trial the efficacy estimand may be more appropriate than the effectiveness estimand, since it is not confounded by the effects of changing treatment from the randomised treatment to other treatments.

Sensitivity analyses for the secondary estimand

The following sensitivity analyses will be performed:

- The above MMRM analysis will be repeated on the PP using the on-treatment period, as well on the subset of subjects who remains on treatment up until week 26 visit. These analyses will be done to align with the reporting of the phase 3a trials.

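### Starting a barred antidiabetic drug is not handled in the SAP's on-treatment or per-protocol definitions, so the analyses supporting non-inferiority can retain HbA1c values lowered by that drug

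*Protocol*

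**What the plan says.** **The bar.** Protocol 5.4 lists what subjects should not do after entry, including "start treatment with any other antidiabetic treatment" and changing the dose or frequency of their oral drugs (a decrease for safety is allowed). Section 5.4.1.2 adds that sulfonylureas and glinides must not be initiated during the trial.

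**What happens to trial product.** Protocol 6.6 opens its mandatory list with "The subject must be prematurely discontinued from trial product if the following applies". Item 4 on that list is "Initiation or significant change in concomitant medications for more than 14 calendar days which in the investigator's opinion could affect weight or glucose metabolism". Under Protocol 6.5, after a confirmatory fasting glucose, "If this FPG exceeds the limits described above, the trial product must be discontinued".

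**On-treatment period (SAP 2.3).** "The period starts on day of the first dose of trial product and ends 7 days after last dose of trial product is taken". Other glucose-lowering drugs are not mentioned.

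**PP set (SAP 2.3).** The criteria are the entry criteria, an HbA1c at screening or randomisation, an HbA1c after 12 weeks of exposure, and "Have at least 12 weeks of exposure". Prohibited medication is not among them.

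**Analyses (SAP 2.4).** The secondary (de jure) estimand uses an MMRM on FAS on-treatment data. The PP check of the primary estimand repeats the primary analysis, which uses in-trial data, including week 26 values after treatment discontinuation. The 0.4% penalty applies only to IDegAsp subjects who discontinued or have no week 26 value. The SAP says the efficacy estimand may suit a non-inferiority trial better, "since it is not confounded by the effects of changing treatment from the randomised treatment to other treatments".

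**The concern.** A subject on IDegAsp who adds a barred drug, goes on injecting trial insulin and has a week 26 HbA1c is on-treatment, is per protocol and carries no penalty. The HbA1c reduction from the added drug is then credited to IDegAsp in the two analyses meant to show the effect under adherence and without major deviations.

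In a non-inferiority trial, extra glucose lowering in the weaker arm pulls the difference towards zero. The primary analysis accepts this by design, since its estimand takes subjects as they are. The PP and MMRM results are there to show whether the conclusion survives without such influences. If barred use is more frequent on IDegAsp, their agreement with the FAS could be partly an artefact of data they were expected to leave out.

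**Working it through.** **1. The plan's own sample size.** With one-sided 2.5%, SD 1.3, margin 0.40 and a two-sample t-test:
- FAS: distance to margin 0.40 − 0.06 = 0.34. This gives 264 per arm, 528 in total, power 85.1%. The plan states 528.
- PP: 0.40 − 0.0222 = 0.3778. This gives 214 per arm, and 428 / 0.90 = 475.6, so 476. The plan states 476.

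Both reproduce, so the same SD and set sizes are used below.

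**2. Where barred use leaves data in.** The drug is started before week 26 while trial product is being taken, and week 26 HbA1c is available.

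| Case | MMRM, on-treatment | PP repeat of primary analysis |
|---|---|---|
| 6.6 item 4 applied, under 12 weeks of exposure | Out from 7 days after last dose | Not in PP |
| 6.6 item 4 applied, at least 12 weeks of exposure | Out from 7 days after last dose; earlier values stay | Stays in; 0.4% penalty on IDegAsp only |
| Not stopped (use of 14 days or less, drug not judged relevant, or rule not applied) | Stays in | Stays in if at least 12 weeks of exposure; no penalty |

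In the second row, equal use in the two arms cancels the drug effect and leaves the penalty, which works against IDegAsp. The third row is the one that can favour IDegAsp without any offset.

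**3. Size, under assumptions.** The documents give no rate of barred use and no add-on effect. Assumed: add-on effect 0.8% HbA1c, fully additive, in subjects who keep a week 26 value and carry no penalty; excess use on IDegAsp of 3, 5 or 6 percentage points; true difference at the margin, D = 0.4.
- Shift = excess use × 0.8
- SE = 1.3 × √(2/n)
- Nominal one-sided error = Φ(shift/SE − 1.96)

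Set sizes: PP 264 × 0.90 ≈ 237 per arm, SE 0.119. On-treatment at week 26: 264 × 0.85 ≈ 224 per arm, SE 0.123. The latter is a simple t-test stand-in for the MMRM.

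| Excess use | Shift | PP error | On-treatment error |
|---|---|---|---|
| 0 | 0 | 2.5% | 2.5% |
| 3 points | 0.024 | 3.9% | 3.9% |
| 5 points | 0.040 | 5.2% | 5.1% |
| 6 points | 0.048 | 6.0% | 5.8% |

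With half the effect (0.4%), the shifts are 0.012 to 0.024 and the errors 3.1 to 3.9%. Over a wider grid (2 to 10 points, effect 0.5 to 1.0%), the shift is 0.01 to 0.10 and the error about 3 to 13%. More use in the comparator arm moves the result against IDegAsp.

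**4. Power after the fix.** Dropping 0, 2, 5 or 10% of the PP set leaves 237, 232, 225 or 213 per arm and power of 88.4, 87.8, 86.8 or 84.9%. Dropping the same shares of on-treatment week 26 values leaves 224, 219, 213 or 201 per arm and power of 90.1, 89.5, 88.7 or 86.8%.

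**The case against.** **The protocol already stops most such subjects.** Section 6.6 item 4 is mandatory, and rescue also stops trial product before alternative therapy. Either stop ends the on-treatment period and, in the IDegAsp arm, brings the penalty. This stands for the MMRM. A reader might infer that barred use never ends on-treatment data; the documents do not support that. Item 4 does, however, depend on the investigator's opinion in an open-label trial, and the SAP has no rule for the case where the stop was due and did not happen. For the PP repeat, the stop does not remove the subject.

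**The error rate of the trial is not at stake.** This stands. SAP 2.4 bases the non-inferiority conclusion on the FAS and the primary estimand, which include such values on purpose. The error figures above must not be read as inflation of the trial's 2.5%.

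**The SAP does not contradict itself.** A reader might take its sentence on confounding as a claim of freedom from all other treatments. It speaks only of changing from randomised to other treatment, and the definition delivers that. The mismatch is with the de jure estimand in SAP 2.1, which supposes adherence to treatment.

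**There is a review before database lock.** SAP 2.3 lets the study group exclude subjects or observations with documented reasons, and Protocol 19.1 requires deviations to be recorded. This helps, but it is discretion with no stated criterion for barred drugs.

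**The size is speculative.** The use rates are assumed. Weekly titration to a common fasting target, with no maximum dose, means an added drug would partly displace insulin, so a fully additive 0.8% is likely an upper value. This stands.

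**A PP exclusion can itself bias.** Starting an add-on follows randomisation and is likely linked to poor control. Removing such subjects can take poor responders out of the weaker arm. This also stands.

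**Conclusion.** The gap is real but narrower than the definitions suggest when read alone. For the MMRM it comprises barred-drug users who are not stopped, plus values between the drug's start and 7 days after the last dose. For the PP repeat it also includes correctly stopped subjects with at least 12 weeks of exposure. The primary conclusion is untouched; what suffers is the independence of the supporting evidence.

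The illustrated size, a shift of 0.024 to 0.048% HbA1c and a nominal error of about 4 to 6% in those analyses, rests on an assumed 0.8% effect and an assumed excess of 3 to 6 percentage points on IDegAsp among subjects not stopped. With equal use among such subjects there is no shift. The SAP should be changed because the remedy is cheap and replaces discretion in an open-label trial with a rule.

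**What to change.** In SAP 2.3 and 2.4:
1. For the HbA1c analyses of the secondary estimand, end on-treatment data at the earlier of (a) 7 days after the last dose of trial product and (b) the first day of an antidiabetic drug barred by Protocol 5.4 or 5.4.1.2, or of an oral antidiabetic dose increase, lasting more than 14 days. Later values are treated as missing in the MMRM.
2. Add the same event, if before week 26, to the PP exclusions.
3. Report its frequency by arm, which shows directly whether the concern arose.

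The wording should count only events that begin while trial product is being taken. Alternative therapy prescribed after a stop, and the protocol's washout insulin, are not barred use. Use of 14 days or less stays outside the rule.

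**Cost.** SAP text and a derivation from antidiabetic start and stop dates and daily doses already collected under Protocol 8.2.5. No clinical rule and no sample size changes; at 5% removed, power is 86.8% for PP and 88.7% for on-treatment data. The downsides are slightly fewer subjects or values, reliance on missing at random after the cut, and possible post-randomisation selection in the PP set. PP should therefore be read beside the MMRM and the FAS result, not alone.
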